1. BACKGROUND

1.1.Summary

Oral fluid based self-testing provides another option to increase the uptake of HIV testing. Studies have shown that interest and acceptability of self-testing with oral fluid is high.^{1–}

Version 1: 13-Jul-2021

Despite significant progress made in improving testing rates over time, concern has been raised that conventional, public, facility-based testing has several weaknesses, including long waiting time, repetitive counselling, the identification of HIV negative people within the testing program without a subsequent effective prevention message, poor quality control on the part of testers in terms of test administration, and the inability to reach key and vulnerable populations.^{3,4} Self-Testing for HIV ("HIVST") is an emerging approach with the potential to increase the uptake of HIV testing to be high impact, low cost, and empowering for those who may not otherwise test, notably in key populations and other people at high risk for HIV infection.⁵ This technological innovation in the healthcare industry may be considered a disruptive innovation technology, as it brings to the market an innovation that may be affordable, simple, accessible and convenient if successful. There is a growing body of supporting evidence showing the acceptability and usability of HIVST in various key populations and groups^{2,5,6} with further plans for evaluations on device performance.

1.2. Device Description

OraQuick® HIV Self-Test

OraSure Technologies, Inc. has developed packaging and labeling for use of a variation of the OraQuick *ADVANCE*[®] Rapid HIV-1/2 Antibody Test in a self-test environment. This product is known as the OraQuick HIV Self-Test. It is comprised of the same components as the current OraQuick *ADVANCE*[®] Rapid HIV 1/2 Antibody Test available in the United States. The test is packaged and labeled for consumer use. The OraQuick HIV Self-Test is a single-use, qualitative immunoassay to detect antibodies to Human Immunodeficiency Virus Type 1 (HIV-1) and Type 2 (HIV-2) in oral fluid.

The OraQuick® HIV Self-Test is a visually read, qualitative, in vitro lateral flow immunoassay for the detection of antibodies to HIV-1 and HIV-2. An oral fluid specimen is collected using the flat pad on the test device, followed by the insertion of the test device into the vial of developer solution.

The OraQuick® HIV Self-Test package includes a specific, step-by-step instructions and a device stand. The actual device and developer vial are not different from the OraQuick *ADVANCE®* Rapid HIV-1/2 Antibody Test (not currently available for commercial use in Canada). The difference is in the packaging and labeling which were specifically designed

CONFIDENTIAL Page 7 of 45

for consumer use. This packaging, along with the instructions for reading and interpreting the results and all accompanying materials, will be used in this study.

1.3. Clinical Studies of Investigational Device

The OraQuick® HIV Self-Test packaging is the result of a development effort that incorporated investigator feedback and data collected during clinical investigations of usability, self-test accuracy, and linkage into care which is licensed under the US FDA. See additional information for:

- Approval of OraQuick ADVANCE Rapid HIV-1/2 Antibody Test (June 22, 2004)⁷
- Approval of OraQuick In-Home HIV Test (July 3, 2012)⁸
- Summary of WHO prequalification assessment for OraQuick HIV 1/2 Self-Test (November 2019)⁹

According to a report published by UNITAID in July 2017, an individual's knowledge of their and their partner's HIV status is essential to the HIV response. Despite the many benefits of HIV testing, in 2016, approximately 30 per cent of people with HIV globally, (and up to 14% in Canada), remained unaware of their status. Some of the largest gaps in testing, prevention and treatment coverage are among men who have sex with men, Indigenous communities, people who use drugs, young people and other key populations who are often reluctant or unable to access existing services. People who use drugs, young people and other key populations who are often reluctant or unable to access existing services. Recognizing this, the World Health Organization (WHO) recommended that HIVST be offered as an approach to complement existing HIV testing approaches, and subsequently released the guidance document TSS-1 Human Immunodeficiency Virus (HIV) rapid diagnostic tests for professional use and/or self-testing in 2016. Since then, HIVST has been scaling up rapidly in global settings.

CONFIDENTIAL Page 8 of 45

1.4. Summary of Known Benefits and Risk of HIV Self-Testing

The potential benefits of an HIV Self-Test include immediate and private test results, which may encourage testing of individuals or high-risk groups who may otherwise refrain from testing due to privacy issues and stigma.

Version 1: 13-Jul-2021

While many governments offer free testing for HIV in a clinic setting, the ability to self-test removes the need for time spent visiting a clinic and waiting for results, particularly important where public testing facilities are long distance; many people who make the effort for clinic-based testing often fail to return to receive their test results (both positive and negative). Additionally, private HIV testing can reduce the burden for routine testing for negative or sero-discordant partners, resulting in more people knowing and monitoring their HIV status over time.

Providing individuals with a tool to test themselves could also lead to earlier diagnosis of HIV status, with the potential for earlier medical intervention through both digital health technologies/telephone held lines as well as clinic follow-up for confirmatory testing. With an earlier diagnosis, individuals are empowered to modify their high-risk behaviours, potentially reducing the number of new HIV infections. This empowerment of consumers is not only limited to modification of lifestyle decisions, but also in being proactive in their health-care decisions.

The potential risks of an HIV Self-Test include not understanding the limitations of a screening test, such as use of the test during the window period of seroconversion, or receiving a false positive, false negative, or invalid test result. HIV Self-Tests can be used without a counsellor present, with the potential for adverse outcomes if the user obtains an unexpected result. As far as possible, these risks are identified in the HIV Self-Test instructions for use (IFU; see Appendix A), with instructions on when not to use the test, how to interpret the test result, and what to do next for a positive, negative or invalid result.

Additional risks of HIV Self-Testing include the inability to track individuals for medical follow-up, partner notification, and public health reporting. There is also the potential for coercive testing and testing by unprepared minors. All of these possible risks are being addressed in various forums where experts are developing guidance around HIV Self-Testing.

Participants may experience slight temporary discomfort where the gums are swabbed during the OraQuick® HIV Self-Test.

Although every effort to protect participant privacy and confidentiality will be made, it is possible that participants' involvement in the study could become known to others, and that social harm may result (i.e., because participants could become known as HIV-infected or at "high risk" for HIV infection).

CONFIDENTIAL Page 9 of 45

1.5. Study Compliance Statement

This study will be conducted in compliance with The Canadian Medical Research Council Guideline on the "Code of Ethical Conduct for Research Involving Humans" and according to the general requirements of the International Conference on Harmonisation harmonised tripartite guideline E6 (R1): Good Clinical Practice.¹³

Version 1: 13-Jul-2021

2. STUDY OBJECTIVES

The primary objectives of this study will be to:

- 1) Evaluate the device performance, i.e. sensitivity and specificity, compared to laboratory reference testing
- 2) To document if intended users (non-professional "lay users"), can successfully perform the steps to use the OraQuick® HIV Self-Test, without product familiarization or demonstration (accuracy/usability)
- 3) To document if intended users, (non-professional "lay users"), can successfully interpret contrived strong positive, weak positive, negative, and a range of invalid results (test results interpretation) and
- 4) To document if intended users can understand the key messages in the labeling (label comprehension).

3. STUDY DESIGN

3.1. Overall Study Design

[figure not shown]
This is a cross-sectional study that employs both observational and interview-based methods.

A minimum of 900 lay participants (non-healthcare professional and inexperienced in HIV self-testing) will read the instructions for use (IFU) and conduct the OraQuick® HIV Self-Test. They will not be provided any training prior to use of the test. A trained healthcare provider or researcher (trained Observer) will watch, and document use of the test and independently read the participants self-test result. The participants will then complete a questionnaire to share their opinion on usability and label comprehension of this test. A minimum of 400 participants will also be provided five mock devices with different results and asked to interpret those results i.e. strong positive; weak positive, negative, invalid with no control and no test line, and invalid with no control and a positive test line.¹⁴

All participants will also have a venous blood sample collected for testing of plasma at a central laboratory with a 4th generation HIV enzyme immunoassay (EIA) that will serve as the Comparator Method (CM). All self-tests will be confirmed using a Canadian standard HIV testing algorithm. The sensitivity and specificity of the self-test result will be calculated relative to the "clinical truth" of the participants' HIV status determined by the confirmatory test process, where applicable. Participants will be instructed to return to the clinic for a follow-up visit, two (2) weeks after self-testing to obtain their laboratory test results which will be their official result.

CONFIDENTIAL Page 10 of 45

Flowchart representation of the overall process from recruitment through Confirmatory testing:

CONFIDENTIAL Page 11 of 45

3.2. Study Population

In this study, eligible participants will be those eighteen (18) years or older, of any race or gender. The population will be comprised of a minimum of 900 participants with unknown HIV status (never tested or last known HIV negative test must be a minimum of 3 months prior), including 400 participants at risk for HIV infection e.g. injection drug users (IDU), men who have sex with men (MSM), etc. These participants will be recruited from geographically distinct study sites to represent an ethnic, genetic and HIV risk diverse population across Canada.¹⁴

Version 1: 13-Jul-2021

3.3. Study Sites

The study will be in up to seven (7) sites across Canada, along with regions utilizing their provincial laboratories, where available. These sites will include clinics that provide services to individuals from high-risk populations such as IDUs, MSM, and members of the African, Caribbean and Black (ACB) and Indigenous communities. This will ensure that we reach our quota of high-risk persons.¹⁴ All study procedures will be conducted under the supervision of the local site principal investigator or his/her designee.

Note: The study sites will follow all appropriate safety requirements that are in place during entire study conduct, to ensure the safety of all participants and the healthcare providers. This will include the use of any appropriate personal protective equipment (PPE), as recommended by each provincial jurisdiction.

3.4. Study Description

Usability

The self-test portion of the study will be performed on consenting persons (referred to as participants) and will include recruitment of participants who have consented to be tested for HIV as per the test procedures outlined.

The participant will be evaluated for the self-test process success or difficulty by a silent, non-interacting trained healthcare professional / researcher (Observer) in the same room. Overall processes include self-test Usability (observation to determine if participants perform all critical steps correctly), Results Interpretation (confirmation by observer to determine if participant interprets test results correctly), and Label Comprehension (questionnaire to determine that the participant is aware of test limitations and what to do following the test result). Successful completion of these tasks will be evaluated as a percentage of the overall process, with all critical errors identified.

Each participant will obtain an oral fluid specimen and perform the test, including result interpretation, according to only those materials provided with the OraQuick® HIV Self-Test (e.g. instructions for use).

Each self-test will be observed by trained healthcare professional/ researcher (referred to as Observers). The Observer does not tutor or interact with the participant conducting the self-test but notes errors and other observations about the participant.

CONFIDENTIAL Page 12 of 45

The Observer also interprets the test result, immediately after the participant and within the validated reading time stated in the instructions for use and records the result separately.

Version 1: 13-Jul-2021

All participants will have a venous blood sample taken (typically from the forearm; up to 7mls or about 1.5 tablespoons) and sent to a local provincial laboratory for HIV EIA testing. The laboratory portion of the study will conduct Comparator Method ("CM") testing on plasma from venous blood samples collected from study participants with Health Canada licensed HIV-1/HIV-2 combination antigen/antibody test that is in routine use in the participating local laboratories. Results of all laboratory testing will be shared with the intended use sites since the lab test will serve as the standard of care test.

Sites will be using their local lab or arrange to have samples sent to a lab that uses the same comparator assay.

Results from the lay user OraQuick® HIV Self-Test will be compared to the laboratory HIV EIA testing.

Subsequent care decisions will be based solely on the results of the study site's standard of care test, not on the OraQuick® HIV Self-Test result.

Readability

Participants will also be provided five (5) mock devices with different results and asked to interpret those results. These responses will document whether intended users, (non-professional and inexperienced in HIV self-testing), can successfully interpret contrived strong positive, weak positive, negative and a range of invalid results.

The participants will then complete a questionnaire (see Appendix G) to share their opinion on usability of this test.

3.5. Selection and Withdrawal of Participants

3.5.1. Inclusion/Exclusion Criteria

Participant's eligibility to enroll will be based upon inclusion and exclusion criteria and the signing of informed consent. The requirements for inclusion/exclusion are as follows:

Inclusion Criteria

Participants considered eligible for inclusion are those who:

- 1. Are 18 years of age and older
- 2. Are able to speak / read / write English or French
- 3. Have presented for voluntary testing for HIV infection in the clinic or community based setting
- 4. Are willing to participate in the study site's standard of care HIV counselling and testing program and receive the study site's standard of care test results
- 5. Are willing to be a participant in the study
- 6. Are able to provide informed consent i.e. understands and signs the informed consent form

CONFIDENTIAL Page 13 of 45

- 7. Are able to complete the required testing on the allocated testing day
- 8. Are willing to provide the necessary oral fluid and venipuncture blood for use in the study protocol testing methods.

Version 1: 13-Jul-2021

9. Are of unknown HIV status (last HIV negative test must be a minimum of 3 months prior)

Exclusion Criteria

Participants considered ineligible for participation in the study are those who meet any of the following exclusion criteria:

- 1. Do not meet all the inclusion criteria
- 2. Are known HIV positive
- 3. Are on antiretroviral therapy (ART) or anti-HIV medications for the treatment of HIV, either as pre-exposure prophylaxis (PrEP), post-exposure prophylaxis (PEP) or experimental vaccine
- 4. Have any experience or have ever conducted a rapid diagnostic self-test for HIV or any other infectious disease
- 5. Are currently participating in a concurrent trial of HIV self-tests
- 6. Are investigator site employees or immediate family members of sponsor or investigator site employee
- 7. Are a practicing medical healthcare professional (doctor, nurse or HIV counsellor that performs HIV testing with Rapid Tests)
- 8. Any condition which, in the opinion of the Observer, would make the participant unsuitable or unsafe for enrolment or could interfere with the completion of the assessment and questionnaire etc. or bias the outcome, e.g. being unable to see / read by forgetting to bring reading glasses, being intoxicated, acute sickness, visibly distressed.

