4.3 Enrollment Questionnaire - Review Eligibility Criteria

Participants providing informed consent and meeting inclusion criteria may be eligible to participate in the study. Participants will be administered an Enrolment Questionnaire to ascertain successful qualification for enrolment (Appendix C). The questionnaire clearly outlines the inclusion and exclusion criteria. If participants satisfy all the inclusion criteria and none of the exclusion criteria, eligibility for enrolment can be confirmed. All participants evaluated for participation in this study will be assigned a unique participant identification number (PID number). Enrolment questionnaires will capture information such as PID Number, Age, Nationality and Employment status. Participants that do not satisfy inclusion/exclusion criteria are documented and reported as exclusions. In addition, the reason for the enrolment failure will also be recorded.

The PID number will also be considered the Participant Number, following the format below:

- AA = Study name
- BB = Province of Investigational Site; example ON for Ontario, QC for Quebec.
- CC = Investigational site number identifier
- DDD = Sequential sample identifier, starting at 001 for all participants For example, Self-Test-Ontario-Site#1-Participant#1: ST-ON-01-001:

Multiple copies of pre-printed labels with the PID Number will be provided to the study site facility. These labels will be placed on the forms and whole blood samples.

The enrollment questionnaire will gather the following demographic information:

- Age
- Ethnicity
- Gender
- Experience with HIV testing
- HIV Status/Risk
- Language capabilities
- Visual Status (glasses/contacts)

CONFIDENTIAL Page 16 of 45

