4.10 Observer's Interpretation of Study Participant's Self-Test Result

Following the completion of the study participant's self-testing interpretation, the Observer will make their own interpretation of the study participant's test result. This should be the site staff who observed the study participant's self-test. Data to be collected will be:

• The Observer's interpretation of the study participant's self-test result.

The Observer's interpretation of the study participant's self-test is intended to allow for review of the data regarding study participants' potential failure to obtain a result versus incorrect interpretation of the result they do obtain.

In the case of a truly invalid test by the study participant, the test will not be repeated.

CONFIDENTIAL Page 20 of 45

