5.2 Trained Researcher/ Observer Responsibilities

The site will provide a minimum of two (2) trained Observers responsible for enrolling eligible participants, collecting samples, and running, interpreting, and documenting the results of the OraQuick® HIV Self-Tests. Prior to the beginning

CONFIDENTIAL Page 23 of 45

of the study, all trained observers will receive appropriate training that covers study procedures, as well as, instructions for performing the test.

Version 1: 13-Jul-2021

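### Exclusion 8 lets the role that scores the self-test turn people away for expected non-completion or difficulty, so it can remove likely failures from the results for objectives 2 to 4

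*Combined protocol and SAP*

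**What the plan says.** Section 3.5.1, exclusion 8, covers "Any condition which, in the opinion of the Observer, would make the participant unsuitable or unsafe for enrolment". It then adds a second ground, a condition that "could interfere with the completion of the assessment and questionnaire etc. or bias the outcome". Its examples are "being unable to see / read by forgetting to bring reading glasses, being intoxicated, acute sickness, visibly distressed", offered as illustrations and not as a complete list.

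Section 5.2 asks each site for at least two Observers, "responsible for enrolling eligible participants, collecting samples, and running, interpreting, and documenting" the self-test results. Section 3.4 has the Observer score the session: "The Observer does not tutor or interact with the participant conducting the self-test but notes errors and other observations about the participant". Section 4.10 gives the independent reading of the device to the person who watched: "This should be the site staff who observed the study participant's self-test".

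Section 2 makes performing the steps, interpreting contrived results and understanding the label primary objectives 2, 3 and 4. Section 6.6 classes ending the process early as a critical error, and section 4.9 has uncompleted tests documented. Section 4.9 also has the participant's distress rated during the test, up to the level where staff must step in.

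On exclusions, section 4.3 has people who fail the criteria documented and reported, and states: "In addition, the reason for the enrolment failure will also be recorded". Nothing in section 6 uses those records.

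**The concern.** In a usability study, a user who struggles or gives up is a result. A criterion that turns people away because they might not finish, or might shift the outcome, permits selection on the predicted value of the endpoint. It rests on opinion, has no threshold, and is applied by a role that also scores the session. If people with a lower chance of success are turned away, they leave the denominators of three primary objectives. The observed success rates then describe a group more able than the HIV-testing population that section 4.1 says participants will represent. Up to seven sites may apply an opinion-based rule differently, and no planned analysis would show how far the results depend on it.

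**Working it through.** **1. The text.**

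- *Ground for exclusion:* a condition that might interfere with finishing the assessment and questionnaire, or bias the outcome (3.5.1).
- *Outcomes:* performing the steps, interpreting results, understanding the label (section 2); early termination is a critical error (6.6).
- *Who decides and who scores:* the Observer enrols (5.2), notes errors (3.4) and reads the device (4.10). No section requires the one who screens to differ from the one who scores, and none says they are the same person.
- *Timing:* screening precedes the test, so the decision rests on a prediction and not on a known result.

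The ground and the outcomes overlap, so the rule as written permits exclusion for predicted failure.

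**2. Size, for illustration only.** The plan has no figure to reproduce. Section 4.1 says the study numbers were not computed, and no success rate, exclusion rate or pass threshold is given for objectives 2 to 4. All rates below are assumptions.

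Let f be the share of otherwise eligible people turned away under exclusion 8, p the success rate in those enrolled, and s the rate that those turned away would have had. Then

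inflation = p − [(1 − f)p + f·s] = f × (p − s).

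Example: f = 5%, p = 90%, s = 50% gives 0.05 × (0.90 − 0.50) = 2.0 points. The number turned away per 900 enrolled is 900 × f/(1 − f).

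| f | Turned away per 900 enrolled | p=90%, s=50% | p=90%, s=25% | p=95%, s=50% | p=95%, s=25% |
|---|---|---|---|---|---|
| 1% | 9 | 0.4 | 0.65 | 0.45 | 0.7 |
| 2% | 18 | 0.8 | 1.3 | 0.9 | 1.4 |
| 5% | 47 | 2.0 | 3.25 | 2.25 | 3.5 |
| 10% | 100 | 4.0 | 6.5 | 4.5 | 7.0 |

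Entries in the last four columns are percentage points. If s = p, inflation is 0.

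**3. Against sampling error.** The plan names the Wilson 95% interval for sensitivity and specificity (6.3); it is borrowed here as a yardstick.

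- n = 900: 90% has interval 87.9% to 91.8% (half-width 2.0 points); 95% has 93.4% to 96.2% (1.4 points).
- n = 400, the mock-device number: half-widths are 3.0 points at 90% and 2.2 points at 95%.

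The share at which the bias equals the distance to the lower limit is f = (p − lower limit)/(p − s). At n = 900:

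- p = 90%, s = 50%: (0.9000 − 0.8787)/0.40 = 5.3%, about 51 people per 900 enrolled.
- p = 95%, s = 25%: (0.9500 − 0.9338)/0.70 = 2.3%, about 21 people per 900 enrolled.

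At n = 400 the same two cases need 8.3% and 3.7%. At f = 1% the largest inflation in the table is 0.7 points, half of the narrower n = 900 half-width.

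**4. Extreme bound.** Take 810 successes in 900 (90.0%) with 47 turned away. Counting all 47 as failures gives 810/947 = 85.5%, a drop of 4.5 points. Assuming 50% success among them gives a drop of 2.0 points. The first figure is a limit and not an estimate, because these people never opened a kit.

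**The case against.** The strongest reply is that exclusion 8 is an ordinary clause for people unfit to take part that day. Its four examples are temporary states. None is low literacy, low education, age or poor dexterity, and the plan keeps such people in view: reading or writing impairment is background data (4.4), visual impairment is recorded (4.5), and education and literacy are possible subgroups (6.4). This stands as to likely use. It does not settle the matter, because the list of examples is open and the ground itself refers to completion and outcome.

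A reader might infer that the selection would be hidden. The documents do not support that. Section 4.3 has exclusions reported with reasons, and every person evaluated receives a number that carries the site, so counts by reason and site can be derived. What is missing is any link from those counts to the results for objectives 2 to 4.

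A reader might also infer that the individual who screens a participant then scores that participant. The documents show a shared role, not a shared person.

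It can also be said that rating distress during the test and judging suitability at enrolment are different moments, and that both can stand. That is fair, but the plan does not say how distress seen before the test is to be separated from distress meant to be observed.

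Finally, deleting only the completion and outcome ground would change little, because the word *unsuitable* is just as open. That is correct, and the fix covers it.

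**Conclusion.** The point holds as a defect of the rule: as written, it permits exclusion on predicted performance for three primary objectives. Any resulting bias would be upward, provided that those turned away would have done worse than those enrolled.

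The tempting stronger conclusion, that the usability, reading and label results are inflated, is not supported. The documents give neither the number who will be turned away nor their likely success rate. The effect may be near zero if the rule is confined to states like the examples. On the assumed rates it is small against sampling error when about 1% are turned away. It reaches the lower confidence limit at n = 900 only at about 2.3% to 5.3%. These results are descriptive and no pass threshold is stated, so no planned decision is shown to change. The case for acting is that the wording conflicts with the objectives and is cheap to correct.

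**What to change.** 1. In exclusion 8, delete the ground about completing the assessment or biasing the outcome, and the open term *unsuitable*. Limit the criterion to a closed list of reasons unrelated to expected performance: safety, inability to consent that day, and a reading aid not at hand. The last does affect performance, but it is an accident of the visit and not a trait of the user.
2. Require the decision and its reason to be recorded before the kit is handed over. Because section 6.3 drops eligibility violations from sensitivity and specificity, this also prevents the criterion from being applied after a result is known.
3. Beside the results for objectives 2 to 4, tabulate criterion-8 exclusions by reason and site. Label any figure that counts them as failures as an extreme bound.
4. Reconcile visible distress as an exclusion example (3.5.1) with distress as a planned observation (4.9).
5. Optionally, have a different Observer screen where one is available. Section 5.2 requires two per site but not two per session, so making this mandatory could need extra staff.

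The cost is one reworded criterion, one timed entry on the enrolment form and one table from data that section 4.3 already collects. The downside is a few more incomplete sessions, which count as failures.
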